## **6.2.2 PrEP Comparison Component Infant Birth and PP Week 6, 14 and 26 Visit**

Infants born to women in the PrEP Comparison Component (both cohorts) will be evaluated for safety at four time points: birth and Weeks 6, 14 and 26 after birth. The date of birth is considered Day 0 and subsequent visits will be calculated from this date. These time points correspond to the maternal labor and delivery visit and maternal postpartum follow up visits at Weeks 6, 14 and 26. Whenever possible, infant visits should be scheduled on the same date of the associated maternal visits.

### **6.2.2.1 PrEP Comparison Component Infant Birth Visit**

The allowable window for all evaluations expected at birth is within 14 days after birth; however, it is understood that sites may not be able to conduct the DXA scan on the same date as the other evaluations and may not be able to arrange a scan within that window. Sites should make every effort to schedule the DXA scan to take place within the 14-day window, but up to 21 days is allowed. See [Section 6.14](#) for further details.

PrEP Comparison Component Infant Birth Visit Procedures (Birth +14 days)		
Clinical		

• Obtain birth history, interim medical and medications history since birth, and feeding history since birth

• Perform complete infant physical exam

Laboratory	Blood	Collect blood for: 

• Creatinine

• TFV-DP level (DBS) (for storage)

	Other	

• Rectal swabs or fresh stool for microbiome

Other		DXA scan of: 

• Whole body

• Lumbar Spine

### **6.2.2.2 PrEP Comparison Component Infant PP Week 6 and PP Week 14 Visits**

Study visits will be conducted six and fourteen weeks following birth for the infant ( $\pm$  14 days). Whenever possible, infant visits should be scheduled on the same date of their associated maternal visits.

PrEP Comparison Component Infant PP Week 6 and PP Week 14 Visit Procedures (<math>\pm 14</math> days)	
Clinical	
 
• Perform targeted physical exam
 
• Obtain interim medical/medications history and feeding history
 

Laboratory	
 
• Rectal swabs or fresh stool for microbiome
 

### 6.2.2.3 PrEP Comparison Component Infant PP Week 26

The final study visit will be conducted 26 weeks following birth for the infant ( $\pm 14$  days). Whenever possible, infant visits should be scheduled on the same date of their associated maternal visits.

PrEP Comparison Component Infant PP Week 26 Visit Procedures (Week 14 <math>\pm 14</math> days)	
Clinical	
 
• Perform complete infant physical exam
 
• Obtain interim medical/medications history including feeding history
 

Laboratory	Blood Collect blood for: 
 
• Creatinine
 

	Other 
 
• Rectal swabs or fresh stool for microbiome
 

Other	Radiology DXA scan of 
 
• Lumbar spine
 

### 6.2.3 Management of Maternal Participants Who Subsequently Switch from Choice Made at Enrollment During the PrEP Comparison Component

All participants enter the study on Step 1; however, the study will accommodate maternal participants who change their minds after enrollment about whether to receive PrEP. Management of these participants will be different depending on the cohort to which they were originally enrolled.

#### 6.2.3.1 Maternal Participants in Cohort 1 Who Subsequently Stop PrEP

To the extent possible, staff should try to identify the reasons for maternal participants choosing to stop PrEP. Once the maternal participant has stated that she is not willing to continue PrEP and the decision to stop PrEP will be entered into an eCRF. If not already required for the study visit at which this decision is made, the following additional study procedures should be conducted:

- iNSC
- TFV-DP level (DBS)
- HIV RNA test

This will not constitute a change from Cohort 1 to 2; the maternal participant will continue to be followed as per her original assignment per [Appendix IIA](#) with the exception of the following evaluations:

- iNSC with drug level feedback

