**SCHEMA – PrEP Comparison Component**

**Purpose:** To determine among young HIV-uninfected women and their infants, the feasibility, acceptability, and safety of oral pre-exposure prophylaxis (PrEP) during pregnancy and postpartum.

**Design:** Parallel observational cohort study

**Study Population:** Pregnant HIV-uninfected women, 16-24 years of age, with a confirmed singleton pregnancy of 32 weeks' gestation or less, and their infants.

Cohort 1: Woman accepts PrEP initiation during pregnancy at study entry  
Cohort 2: Woman declines PrEP initiation during pregnancy at study entry

**Sample Size:** Approximately 350 women to achieve at least 300 evaluable (200 in Cohort 1 and 100 in Cohort 2) and their infants.

**Study Intervention:** *Both cohorts:*  
1. Behavioral HIV risk reduction package, including cohort-appropriate SMS messages throughout follow-up.

*Cohort 1 only:*  
1. Daily oral PrEP (200 mg FTC/ 300 mg TDF) throughout follow-up.  
2. Enhanced adherence support, including SMS messaging and feedback of drug levels with tailored counseling.

**Study Duration:** Approximately 24 months total for this component. Women will be accrued over a 12-month period (from the date of first enrollment) and followed through 26 weeks postpartum. For each woman, the duration of follow-up is expected to range from seven to 12 months depending on gestational age at entry. For each infant, the expected duration of follow-up is approximately six months.

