The primary objectives focus on women who initiate PrEP during pregnancy and continue through the first 26 weeks postpartum (Cohort 1). Adherence to PrEP will be assessed in this population by measuring TFV-DP drug levels in dried blood spots. Participants in this arm will receive an intervention designed to promote PrEP adherence, comprised of a) two-way SMS messaging related to PrEP adherence, and b) targeted adherence counseling guided by TFV-DP drug levels from past visits, refer to [Section 6](#). Participants will be contacted and provided with their DBS TFV-DP concentration results, as described in [Section 6.5](#). Less than adequate concentration results are defined during the PK Component by pharmacokinetic parameters established when drug adherence is measured using TFV-DP levels from dried blood spots.

Maternal participants who change their intent regarding PrEP will be allowed to do so. Participants in Cohort 1 who choose to stop PrEP will continue in follow-up undergoing the same procedures. If these participants later elect to resume PrEP, HIV-infection status must be confirmed before resuming PrEP, refer to [Sections 4.2.1](#) and [6.2.3](#). Maternal participants in Cohort 2 who subsequently choose to initiate PrEP will undergo a Step Change, during which eligibility for starting PrEP will be confirmed, refer to [Sections 4.2.3](#) and [6.2.3](#). These participants are referred to as Cohort 2/Step 2 and will follow the procedures for Cohort 1. These switches onto or off PrEP will be considered in the feasibility/acceptability outcomes, refer to [Section 9.2](#). While a formal step change will only be required when those originally declining PrEP later chose to initiate it, there is no upper limit set on the number of switches allowed. Switching will be closely monitored as part of feasibility and adherence outcomes.

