### 9.2.4 Sample Size and Accrual

The PrEP Comparison Component will enroll a total of 350 (233 in Cohort 1 and 117 in Cohort 2) women over a 12-month period. Women will be followed through 26 weeks postpartum. Expected duration of follow-up for a given maternal participant is between 7 and 12 months depending on the gestational age of the pregnancy at enrollment. The following sample size and power calculations assume a final analysis sample of 300 women (200 in Cohort 1 and 100 in Cohort 2). The primary reason for the 2:1 enrollment into the two cohorts was to balance the need for a “No PrEP” comparison group (to provide the background rates for safety outcome measures) with the need for a large enough PrEP group to examine outcomes that would be restricted to women in that group (Adherence). To achieve this sample size at the analysis phase, this study will enroll ~350 women to accommodate a decrease of ~15% due to maternal attrition.

**Table 8** shows the expected precision of a range of PrEP adherence estimates across different sample sizes in Cohort 1. For example, with a sample size of 200 women in Cohort 1, the width of the 95% confidence interval for an estimated adherence rate of 75% is 13%.

**Table 8: Precision (shown as 2-sided 95% confidence intervals) of different estimates of the proportion with good adherence (for illustration, defined as meeting or exceeding the threshold corresponding to protective drug levels of TFV-DP) at different sample sizes for Cohort 1.**

% Adherent	Sample Size in Cohort 1			
	150	200	250	300
50	42-58%	43-57%	44-56%	44-56%
60	52-68%	53-67%	54-66%	54-66%
65	57-73%	58-72%	59-71%	59-70%
70	62-77%	63-76%	64-76%	65-75%
75	67-82%	68-81%	69-80%	70-80%
80	73-82%	74-85%	75-85%	75-84%

**Table 9** below shows the precision of estimates of safety outcomes (e.g. preterm birth) expected with a range of event rates and a sample size of 200 women in Cohort 1 and 100 women in Cohort 2. It is expected that the rates of these outcomes will be low particularly since this is a young group of healthy HIV uninfected women. To that end, a range of AE rates with corresponding confidence intervals is included in the protocol.

**Table 9: 95% Confidence Intervals for different possible event rates of safety outcomes in Cohort 1 (n=200) and Cohort 2 (n=100)**

Event Rate	95% Confidence Interval	95% Confidence Interval
	Cohort 1 (n=200)	Cohort 2 (n=100)
0.5%	(0, 2.8)	(0, 3.6)
2.0%	(0.5, 5.0)	(0.2, 7.0)
4.0%	(1.7, 7.7)	(1.1, 9.9)

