2.1.2 PrEP Comparison Component Study Design

The IMPAACT 2009 PrEP Comparison Component is a parallel observational cohort study. It will assess feasibility, acceptability, adherence to, and safety of PrEP during pregnancy and in the postpartum period among adolescents and young women who are HIV-negative. Women will be screened prior to 32 weeks' gestation and subsequently enrolled in two cohorts: those who choose to initiate PrEP at enrollment (Cohort 1) and those who decline (Cohort 2). Infants will be enrolled *in utero* at the same time the woman is enrolled. A randomized trial in which women were assigned to an arm that would not receive PrEP would be unethical at this time due to the overwhelming evidence supporting the efficacy of PrEP to prevent HIV infection. All women enrolled in the study will receive a standard of care package of HIV prevention services and a study-specific behavioral risk reduction intervention. Additionally, all women will receive support for antenatal, delivery and early infant care through brief motivational-interviewing informed counseling at each study visit and one-way mHealth messaging services. Women who choose to initiate PrEP will be provided PrEP as well as drug-level informed adherence support intervention.

Approximately 350 women will be enrolled to achieve at least 300 evaluable women (200 in Cohort 1 and 100 in Cohort 2) and their infants, defined as completing the week 26 postpartum visit. Women will be accrued over a 12-month period (from the date of first enrollment) and followed through 26 weeks postpartum. For each woman, the duration of follow-up is expected to range from seven to 12 months depending on gestational age at entry. For each infant, the expected duration of follow-up is approximately six months.

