- Other approaches to summarizing the adherence outcome will be considered. This includes an ordinal variable with categories corresponding to different dosing levels (e.g., Below limit of quantification (BLQ), Red, Yellow, Green). For this type of outcome, at each visit that drug levels are measured in DBS, descriptive analyses will summarize the proportion of women in each adherence category (refer to categories in the appendix tables 1-2). For the interim analysis the proportion of women with TFV-DP levels below the limit of quantification (BLQ) at the week 12 visit will be estimated. Additional analyses with other cutpoints (e.g., below vs. above the limit of quantification; red vs. not red) will be considered.
- Women in Cohort 2 who later decide to initiate PrEP will be included in the main estimand. In addition, baseline characteristics, and patterns of adherence and duration on PrEP will be summarized separately for women in Cohort 1 and women in Cohort 2 who later decide to initiate PrEP using the approaches outlined above.
- The following additional descriptive statistics will be calculated: The proportion of women a) with at least one visit with TFV-DP levels corresponding to optimal adherence, b) who had TFV-DP levels corresponding to optimal adherence at all visits while formally prescribed PrEP, c) who had no detectable TFV-DP levels at any visit while formally prescribed PrEP d) who formally stopped PrEP among those who had initiated, including reasons for stopping, characterizing those who stop vs continue. In addition, mean follow-up time and % of follow-up time on PrEP will be summarized.

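### SAP 6.3.1, supplemental item (d), summarises PrEP stopping as a crude stop/continue split although time at risk differs between women and those lost to follow-up are not classified

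*Protocol*

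**What the plan says.** Protocol 6.2.3.1 covers recording only: once a Cohort 1 woman says that she will not go on, "the decision to stop PrEP will be entered into an eCRF", and she stays in follow-up under her original cohort. Nothing is wrong there. The analysis is in SAP 6.3.1, where item (d) of the additional descriptive statistics is the proportion of women "who formally stopped PrEP among those who had initiated, including reasons for stopping, characterizing those who stop vs continue". No person-time, cumulative-incidence or censoring method is named for it.

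The same bullet goes on: "In addition, mean follow-up time and % of follow-up time on PrEP will be summarized". Another supplemental bullet summarises duration on PrEP separately for Cohort 1 and for Cohort 2 women who start later. SAP section 7 lists discontinuation with reasons, restarts, and retention by cohort and visit. Table detail is left to the Analysis Implementation Plan, which was not available.

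On time at risk, SAP 2.1.2 states that "the duration of follow-up is expected to range from seven to 12 months depending on gestational age at entry", and the protocol schema gives the same range. The Adherence Set (SAP section 4) includes Cohort 2 women who start PrEP after entry. On attrition, Protocol 9.2.4 says "this study will enroll ~350 women to accommodate a decrease of ~15% due to maternal attrition".

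Protocol 3.2 adds: "These switches onto or off PrEP will be considered in the feasibility/acceptability outcomes", and refers to Section 9.2. Tables 5 to 7 there list no outcome for stopping or switching.

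**The concern.** The primary adherence estimand in SAP 6.3.1 uses only visits before PrEP is discontinued. It describes women who still choose PrEP and can stay high while others leave, so item (d) is one of the few places where leaving PrEP is quantified.

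A raw proportion over unequal follow-up mixes how readily women stop with how long they were watched. Everyone exits at Week 26 postpartum, so a woman who entered early in pregnancy has more months in which to be recorded as stopping. Any characteristic linked to gestational age at entry can then appear to predict stopping when behaviour is the same. Trimester at enrolment, a stratification factor, is the most directly exposed. Cohort 2/Step 2 starters, if pooled, widen the spread further because they may begin at any stage.

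A second gap is that *continue* has no definition for a woman who leaves the study without a formal stop. If she stays in the denominator as a continuer, the stopping proportion is too low.

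**Working it through.** **Inputs from the documents.** Follow-up of 7 to 12 months (SAP 2.1.2; protocol schema); attrition of about 15%, with 350 enrolled (233 + 117) for 300 analysed (200 + 100) (Protocol 9.2.4).

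**Assumptions.** The documents give no stopping rate, so the monthly stopping hazard h is varied from 1% to 10%.

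**Step 1: reproduce the plan's figures.**
- 300/0.85 = 353 against the stated 350; 300/350 = 0.857, or 14.3% attrition. By cohort, 200/0.85 gives 236 and 100/0.85 gives 118, against 233 and 117. The enrolment target agrees with the stated attrition.
- Entry at 32 weeks with delivery at 37 to 40 weeks, plus 26 weeks postpartum, is 31 to 34 weeks, or 7.1 to 7.8 months. Twelve months (52.2 weeks) with delivery at 40 weeks corresponds to entry at about 14 weeks. The stated range is plausible.

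**Step 2: unequal follow-up.** With a constant hazard, the chance of having stopped by month t is F(t) = 1 − exp(−ht).

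| h per month | F(7) | F(12) | Risk ratio | Odds ratio |
|---|---|---|---|---|
| 1% | 6.8% | 11.3% | 1.67 | 1.76 |
| 2% | 13.1% | 21.3% | 1.63 | 1.81 |
| 5% | 29.5% | 45.1% | 1.53 | 1.96 |
| 10% | 50.3% | 69.9% | 1.39 | 2.29 |

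For the stated range, the risk ratio under a constant hazard cannot exceed 12/7 = 1.71.

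**Step 3: other hazard shapes.** Weibull stopping times, with 10% to 50% stopped at 7 months, give these 12-to-7-month risk ratios:
- shape 0.5 (front-loaded): 1.29 to 1.19;
- shape 1.5 (rising): 2.11 to 1.58;
- shape 2: 2.66 to 1.74.

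**Step 4: drop-outs counted as continuing.** This classification is an assumption. Losing 15% by 9.5 months gives a drop-out hazard c = −ln(0.85)/9.5 = 0.0171 per month. If drop-out is unrelated to stopping, the crude proportion at t is h/(h+c) × [1 − exp(−(h+c)t)], compared with 1 − exp(−ht). Averaged over 7 to 12 months:

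| h per month | Crude | Without drop-out | Difference (points) | Relative |
|---|---|---|---|---|
| 1% | 8.4% | 9.1% | 0.7 | −7.7% |
| 2% | 16.0% | 17.3% | 1.3 | −7.6% |
| 5% | 34.9% | 37.6% | 2.7 | −7.2% |
| 10% | 56.9% | 60.9% | 4.0 | −6.6% |

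With this drop-out, the 12-to-7-month ratio in Step 2 falls slightly, to between 1.61 (h = 1%) and 1.35 (h = 10%).

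**The case against.** **It is a secondary matter.** Item (d) is supplemental and descriptive. No hypothesis, test, power calculation or decision rule uses it, and the primary outcome is the drug level. This stands and limits the weight of the point.

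**Time is already described elsewhere.** Duration on PrEP, percentage of follow-up on PrEP, retention by visit, reasons and restarts are all planned, and the implementation plan may add detail. This stands in part. These summaries describe exposure, but they do not adjust a table comparing women who stop with women who continue.

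**Having stopped by Week 26 postpartum is itself meaningful.** Women who start earlier really do have longer to persist. This is fair for the overall proportion. It does not rescue the comparison of characteristics, where length of follow-up and readiness to stop cannot be told apart.

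**Stopping is reversible.** Switches are unlimited, and time to first stop ignores restarts, whereas percentage of time on PrEP reflects them. This stands, so the two should be reported together.

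**The drop-out effect is small.** Protocol Table 9 gives a 95% interval of 23.7 to 36.9% for a 30% rate with 200 women. A shift of 1 to 4 points is smaller than its half-width of (36.9 − 23.7)/2 = 6.6 points. This stands for the drop-out effect. The follow-up effect is larger and tied systematically to gestational age at entry.

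**Conclusion.** The point holds as a minor one. Item (d) uses a crude split over unequal time at risk and leaves women lost to follow-up unclassified. With identical behaviour and a constant hazard of 1% to 10% per month, a woman followed for 12 months is about 1.4 to 1.7 times as likely to be classed a stopper as one followed for 7, or about 1.2 to 1.3 times if stopping is strongly front-loaded. Counting 15% unrelated drop-outs as continuing lowers the proportion by about 7 to 8% in relative terms, or 1 to 4 points. All these figures rest on assumed hazards, and the ratio compares the two ends of the follow-up range rather than typical early and late entrants.

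Three stronger readings are tempting, and the documents do not support them.
- A reader might infer that early enrollees would look about twice as likely to stop. That treats an odds ratio near 2 as a risk ratio, or needs a hazard that rises over time; under a constant hazard the ceiling is 1.71.
- A reader might infer that the plan counts drop-outs as continuing. The SAP does not say so. Its rule of assuming no event after early exit is written for adverse events (SAP 6.3.2 and 6.3.4).
- A reader might take item (d) for the study's main feasibility result. Neither document gives it that status, and the primary estimand does not depend on it.

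**What to change.** Amend item (d) in SAP 6.3.1 as follows:
- Report the cumulative incidence of first formal stop, timed from PrEP start, censoring at loss to follow-up or the Week 26 postpartum visit. Timing from PrEP start also places Cohort 2/Step 2 starters correctly.
- Add a sensitivity analysis that counts drop-outs as stopped.
- Compare characteristics with a Cox model for time to first stop in place of the stop/continue table.
- Report restarts separately, next to percentage of follow-up time on PrEP.

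The cost is SAP wording and one small extra analysis. No new data are needed: the stop decision is already captured, and the planned percentage of time on PrEP already requires start, stop and restart dates. The SAP already uses person-time and Cox models for adverse events. The downside is that time to first stop does not itself capture restarts, hence the last item.

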#### 6.2.3.2 Maternal Participants in Cohort 2 Who Elect to Begin PrEP during Follow-up (Cohort 2/Step2)

Maternal participants who initially declined PrEP may subsequently inform study staff of an interest in starting PrEP. In preparation of PrEP initiation, evaluations should be performed as per

the Step Change column in [Appendix IIB](#). The Step Change will occur across two visits, Visit 1 and Visit 2. Note that the Step Change Visit 1 may be combined with a regular study visit and procedures combined. The participant may not initiate PrEP until she has been determined to be HIV-uninfected via a rapid test, and has otherwise satisfied the eligibility criteria for a Step Change per [Section 4.2.3](#). Blood collection for baseline TFV-DP drug level evaluation must precede ingestion of the first dose of study drug for Cohort 2/Step 2.

PrEP Comparison Component Step Change from non-PrEP to PrEP Visit 1		
Administrative and Regulatory		
 
Review PrEP Comparison Component follow up and risks
 

Behavioral and Counseling		
 
CASI and COVID-19 questionnaire
 
iNSC [see Section 5.3.2]
 
Assess for social harms [see Section 13.6]
 

Clinical		
 
Obtain interim medical records and medical/medication history
 
Perform targeted physical exam
 

Laboratory	Blood	Collect blood for: 
 
HIV RNA test
 
Store plasma for HIV drug resistance testing
 
CBC with differential
 
ALT, creatinine, and CrCl
 
Hepatitis B surface antigen
 
Glucose (random)
 

	Urine	Collect urine for: 
 
Urinalysis (protein and glucose)
 

PrEP Comparison Component Step Change from non-PrEP to PrEP Visit 2		
Administrative and Regulatory		
 
Complete final eligibility determination and confirmation
 
Complete eligibility checklist, enter checklist data into SES to enter the maternal participant into Step 2, print and file a copy of the confirmation
 

Behavioral and Counseling		
 
CASI and COVID-19 questionnaire
 
iNSC [see Section 5.3.2]
 
Assess for social harms [see Section 13.6]
 

Clinical		
 
Obtain interim medical records and medical/medication history
 
Perform targeted physical exam
 

Laboratory	Blood	Collect blood for: 
 
Rapid HIV test [see Section 6.3 in the event the test is (+)]
 
Baseline TFV-DP level (DBS)
 

	Other	Collect vaginal swab for: 
 
Microbiome
 
 Collect rectal swabs (if consented) for: 
 
Microbiome
 

Study Drug		
 
Prescribe and dispense study drug
 

 Perform prior to step change (entering Step 2)

 Review results prior to prescribing study drug.

 Baseline sample must be collected prior to ingestion of study drug.

The maternal participant should continue with her regular follow up appointments. However, at subsequent visits, the study procedures applicable to Cohort 1 throughout this section and as per [Appendix IIA](#) will be conducted through study exit, and participants will be referred to as Cohort 2/Step 2.

